17.1.9 ADVERSE EVENTS OF POTENTIAL DRUG ABUSE AND DEPENDENCE

AEs associated with potential drug abuse and dependence will be identified as described in [APPENDIX 7](#).

These AEs will be summarized by PT only.

17.1.10 EXTRAPYRAMIDAL ADVERSE EVENTS

Extrapyramidal AEs will be identified by MedDRA SMQ 20000095 Extrapyramidal syndrome as described in [APPENDIX 4](#).

These AEs will be summarized by PT only.

17.1.11 ADVERSE EVENTS EXPLORATORY ANALYSIS

Odds ratios (OR) with 95% CIs and p-values will be provided for all AEs, SAEs, AEs leading to

Document: **CCI**

Author: **PPD**

Version Number: 0.6

Version Date: 30JAN2023

Template No.: CS_TP_BS016 Revision 6

Reference: CS_WI_BS005

Effective Date: 02Dec2019

discontinuation, and AEs relating to extrapyramidal symptoms (EPS) between the two treatment groups using a logistic regression model with treatment and geographic region as categorical factors.

Each subject will be counted only once for each AE type. Categories for each treatment group will be AE vs no AE for each AE type listed above.

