12. SAFETY REPORTING

12.1. Definitions

12.1.1. Adverse Events

An adverse event (AE) is any untoward medical occurrence associated with the use of a drug in humans, whether or not considered drug related.

Untoward medical occurrences that occur between the time of signing the informed consent form (ICF) and first drug administration are pre-treatment events. Those that occur after first administration of study drug are considered AEs.

An AE can, therefore, be any unfavorable and unintended sign (including an abnormal laboratory finding), symptom, or disease occurring after the administration of a medicinal (investigational) product, whether or not considered related to the medicinal (investigational) product. AEs may include the onset of new illness and the exacerbation of pre-existing conditions. AEs will be collected from the signing of the ICF to the last study visit (Visit 18 [Follow-up Visit]).

The Investigator should attempt to establish a diagnosis of the event based on signs, symptoms, and/or other clinical information. In such cases, the diagnosis should be documented as the AE and not the individual signs/symptoms.

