13. TERMINATION OF SUBJECT FROM STUDY/DISCONTINUATION OF STUDY DRUG

13.1. Criteria for Subject Termination

Subjects may be discontinued from study participation / the study drug at any time for any of the following reasons. The possible reasons for termination of study participation / study drug are as follows:

- Adverse event
- Lack of efficacy (specify; eg, no improvement in underlying condition)
- Lost to follow-up (specify)
- Withdrawal by subject (specify)
- Non-compliance with study drug (specify)
- Protocol deviation (specify)
- Death
- Pregnancy
- Other (specify)

If at any time during the course of the study, in the opinion of the Investigator, the subject may no longer safely participate due to a change in medical status (eg, experiences an AE, becomes pregnant), the subject must be discontinued from the study drug. Subjects discontinued from study drug will be discontinued from the study.

The reason for study drug discontinuation will be recorded on the appropriate CRF. In case of death, the date of death should be captured on the CRF.

Subjects who prematurely terminate the study participation will not be replaced.

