15. STATISTICS

15.1. Sample Size

A total of 300 subjects are expected to be enrolled from approximately 50 global sites, including the US and Europe. Subjects will be assigned randomly to receive SEP-363856 or active comparator in an allocation ratio of 2:1. The determination of sample size was based upon clinical considerations. The sample size of 300 subjects will provide approximately 80 subjects who are expected to complete 1 year of treatment with SEP-363856 to support sufficient long-term safety data on SEP-363856.

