15.3.6. Safety Analyses

15.3.6.1. Adverse Events

Both AEs and pre-treatment events will be coded using MedDRA.

The following summaries will be provided by treatment and by MedDRA SOC and PT:

- All AEs (including incidence rate and event count)
- AEs by severity (mild, moderate, severe; including incidence rate)
- AEs by relationship to study drug (related, not related; including incidence rate)

The following conventions will be followed in summarizing AEs:

- For incidence rate summaries, each subject will be counted only once within each SOC and within each PT.
- If a subject reports more than one AE within a PT and/or a SOC, the AE with the highest known severity will be used in the by severity summary. AEs with a missing severity will be assigned to the highest severity.
- For summaries by relationship to study drug, AEs will be grouped as “related” or “not related.” AEs assessed as “possible,” “probable,” or “definite,” will be grouped as “related.” AEs with a missing relationship to study drug will be regarded as related. If a subject reports more than one AE within the same SOC and PT, and any are related, the AE will be summarized as related.

Summaries of serious AEs (SAEs) and AEs leading to discontinuation by treatment will also be provided. All AEs starting after the last dose of the study drug up to 9 days following the last dose will be summarized separately. Data listings of AEs, SAEs, AEs leading to discontinuation, and deaths will be presented.

As exploratory analyses, the odds ratios (OR) with 95% confidence intervals (CI) of all AEs, SAEs, AEs leading to discontinuation, and AEs relating to extrapyramidal symptoms (EPS) between the two treatment groups will be provided.

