17.1 ADVERSE EVENTS AND PRE-TREATMENT EVENTS

Adverse events (AEs) and pre-treatment events will be coded using MedDRA central coding dictionary, Version 22.0.

Any COVID-19 related Adverse Events and pre-treatment events will be identified using a pre-defined search:

Table 2: Predefined search criteria for COVID-19 related adverse events or pre-treatment events.

Lower Level Term	Lower Level Term Code	Preferred Term	Preferred Term Code	Search Criteria for COVID-19 Related Adverse Events or Pre-treatment Events
Coronavirus test positive	1007025	Coronavirus test positive	10070255	Preferred Term Code = 10070255 or 10053983
Coronavirus infection	10051905	Corona virus infection	10053983	

Document: CCI

Author: PPD

Version Number: 0.6

Version Date: 30JAN2023

Template No.: CS_TP_BS016 Revision 6

Reference: CS_WI_BS005

Effective Date: 02Dec2019

Any adverse events related to the Russia-Ukraine geopolitical conflict will be identified by the reported term containing “BCP22”.

AEs are defined as untoward medical occurrences that started at the same time of or after the first dose of study drug. Untoward medical occurrences that started prior to the first dose of study drug are pre-treatment events.

Whenever available, the time information should be accounted for in the derivation of AEs vs. pre-treatment events. In the case where time is not available, untoward medical occurrences that started on or after the day of the first dose of study drug will be considered AEs; those that started before the day of the first dose of study drug will be considered pre-treatment events.

See [APPENDIX 2](#) for handling of partial dates for AEs. In the case where it is not possible to classify an untoward medical occurrence as an AE or a pre-treatment event, it will be classified by the worst case; i.e. AE.

Unless otherwise specified, for the purpose of statistical analysis, the AEs in the 361-304 database which started within 9 days after the last dose of 361-304 study drug, will be used in table summaries. All records in the 361-304 AE database, including those that started beyond 9 days after the last dose of study drug, will be listed in data listings.

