Overall summary of the incidence of all AEs, AEs related to COVID-19, AEs related to geopolitical conflict, study medication-related AEs, severe AEs, serious AEs, AEs leading to discontinuation from study, AEs leading to study medication withdrawal, AEs leading to study medication interruption, AEs leading to dose reduction, AEs leading to dose increase and AEs leading to death will be provided by treatment group. This summary will also be repeated by the geographic region, sex, age group, number of prior hospitalizations for treatment of schizophrenia, duration of schizophrenia, and BMI category subgroups.

Listings will be provided for all AEs, severe AEs, serious AEs, AEs leading to discontinuation from the study, AEs leading to study medication withdrawal, AEs leading to study medication interruption, AEs leading to dose reduction, AEs leading to dose increase, AEs leading to death, AEs of potential drug abuse and dependence and extrapyramidal AEs, and psychiatric AEs leading to discontinuation from the study (PAEDCs), AEs related to geopolitical conflict, AEs related to COVID-19. A listing of pre-treatment events will also be presented. When complete event start date and complete event end date are available, duration of AEs/pre-treatment events will be calculated as: event end date – event start date +

Document: CCI

Author: PPD

Version Number: 0.6

Version Date: 30JAN2023

Template No.: CS_TP_BS016 Revision 6

Reference: CS_WI_BS005

Effective Date: 02Dec2019

1. Duration will be presented in data listings.

For all summaries, each subject will be counted only once within each category (e.g. an AE type, a severity level, a relationship category, a duration of exposure category, a SOC, a high level term (HLT), and a PT). If not otherwise specified, all summaries will present the number and percentage of subjects as well as the number of events. For summaries by SOC and PT, AEs will be sorted by SOC based on the internationally agreed order (see [APPENDIX 10](#)) and then by PT in decreasing frequency in the “SEP-363856 50 to 100 mg/day” column. For summaries by SOC, HLT, and PT, AEs will be sorted by SOC based on the internationally agreed order and then by HLT and PT in decreasing frequency in the “SEP-363856 50 to 100 mg/day” column.

COVID-19 related pre-treatment events and AEs and geopolitical conflict related pre-treatment events and AEs will be displayed similarly as any other pre-treatment events and AEs.

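### The only between-arm AE estimate is an exploratory ever/never odds ratio that ignores follow-up time, although about 60% of SEP-363856 subjects are expected to stop within the year

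*SAP*

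**What the plan says.** The primary endpoint is the incidence of all AEs, SAEs and AEs leading to discontinuation (SAP 2.2.1). SAP 17.1 fixes the form of the tables: "If not otherwise specified, all summaries will present the number and percentage of subjects as well as the number of events".

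The only between-arm AE estimate is in SAP 17.1.11: "Odds ratios (OR) with 95% CIs and p-values will be provided for all AEs, SAEs, AEs leading to" discontinuation and for EPS AEs, "using a logistic regression model with treatment and geographic region as categorical factors". Each subject is coded as having or not having the event. Protocol 15.3.6.1 gives its status: "As exploratory analyses, the odds ratios (OR) with 95% confidence intervals (CI) of all AEs, SAEs, AEs leading to discontinuation", and likewise for EPS AEs. SAP 7.4 makes all p-values nominal.

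Follow-up is tied to treatment. Protocol 13.1: "Subjects discontinued from study drug will be discontinued from the study". Protocol 12.1.1: "AEs will be collected from the signing of the ICF to the last study visit", which is the visit 7 ± 2 days after the last dose. SAP 17.1 limits the tables to AEs "which started within 9 days after the last dose of 361-304 study drug, will be used in table summaries".

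On retention, Protocol 15.1 says: "The sample size of 300 subjects will provide approximately 80 subjects who are expected to complete 1 year of treatment with SEP-363856". No corresponding figure is given for quetiapine XR.

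Kaplan-Meier and log-rank analyses are planned for time to discontinuation (SAP 9) and relapse (SAP 16.2.12), but not for any AE endpoint. Person-years are calculated (SAP 14) but not linked to AEs. SAP 17.1.1.3 tabulates all AEs by exposure at earliest onset, using as denominator the subjects still exposed at the start of each interval.

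**The concern.** The odds ratio gives a subject who stopped after 10 days without an AE the same weight as one who completed 52 weeks without an AE. When most subjects are expected to leave early, the chance of ever having an AE depends on how long the subject stayed as well as on the AE rate. If one arm keeps its subjects longer, it has more time in which to accumulate AEs. The odds ratio can then depart from 1 when the AE rates are equal, or hide a difference when they are not.

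This is a 52-week study of long-term safety, and the odds ratio is its only comparative AE statistic. A reader will take it as a comparison of AE rates. Nothing planned beside it separates rate from retention.

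**Working it through.** **Completion.** The 80 cannot be derived forward, because no dropout rate is given. Back-calculated: 300 × 2/3 = 200 on SEP-363856, and 80/200 = 40%. As a plausibility check, Protocol 4.1 cites 70% to 80% discontinuing before 18 months. Under an assumed constant hazard, 12-month retention is 0.30^(12/18) = 44.8% down to 0.20^(12/18) = 34.2%, or 90 to 68 of 200, which brackets 80.

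**Assumptions.** The documents give no AE rates and no quetiapine XR retention, so these values are assumed. AE hazards are 1.0/year, 0.1/year, or clustered early (6/year for 4 weeks, then 0.2/year). Quetiapine XR retention runs from 55% to 30%. Dropout has a constant hazard d, independent of AEs.

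**Crude percentage on SEP-363856.** d = −ln(0.40) = 0.916/year. For a constant AE hazard L:

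- Observed on treatment = L/(L+d) × (1 − exp(−(L+d)))
- Risk if nobody stopped = 1 − exp(−L)

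The early-clustering row is by numerical integration.

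| AE hazard | On treatment | With 9-day tail | If nobody stopped |
|---|---|---|---|
| 1.0/year | 44.5% | 45.5% | 63.2% |
| 0.1/year | 6.3% | 6.4% | 9.5% |
| Early clustering | 42.6% | 43.4% | 47.6% |

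The SAP tables include the tail, so the relevant gaps are 17.7, 3.1 and 4.2 points. The two left-hand figures are the cumulative incidence with stopping as a competing event. The right-hand figure is a hypothetical quantity.

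**Odds ratio with equal AE hazards** (SEP-363856 retention 40%, no tail). At 1.0/year and 55% retention, the quetiapine XR crude figure is 49.9%, so OR = (0.445/0.555)/(0.499/0.501) = 0.80. The rest follow in the same way. Standard error of log OR = √[1/(200·p(1−p)) + 1/(100·q(1−q))], with p and q the crude proportions on SEP-363856 and quetiapine XR.

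| AE hazard | OR at 55% | OR at 30% | Largest absolute log OR | SE |
|---|---|---|---|---|
| 1.0/year | 0.80 | 1.18 | 0.218 | 0.245 |
| 0.1/year | 0.86 | 1.13 | 0.147 | 0.484 |
| Early clustering | 0.94 | 1.05 | 0.061 | 0.247 |

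With equal retention the OR is 1.00 in every row. The hazard ratio is 1.00 throughout by construction.

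**Do event counts and person-years already suffice?** Take early clustering with equal hazards, and let events recur at the same hazard. At 40% retention, expected events per subject are 5.8 × (1 − exp(−0.916 × 4/52))/0.916 + 0.2 × 0.655 = 0.562 over 0.655 years, or 0.858/year. At 55% retention they are 0.587 over 0.753 years, or 0.779/year. The rate ratio is 1.10 when the truth is 1.00, so a crude rate does not remove the retention effect when AEs come early.

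**Does the onset-interval table suffice?** It accounts for attrition through its denominators. It covers all AEs only, not SAEs or EPS AEs separately. As written, it does not remove subjects who already had the event from later denominators. It gives no between-arm contrast.

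**The case against.** The strongest case on the other side is that this is a descriptive safety study with no hypothesis to test (Protocol 4.4), and the stated endpoint is incidence. Every subject has the event while observed, stops without it, or completes. The crude percentage is therefore already the on-treatment cumulative incidence, apart from the short post-dose tail. That stands. A reader might infer that the percentages understate one-year on-treatment risk. They do not: what they understate is the risk that would apply if nobody stopped, which the plan never claims to estimate.

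It can also be said that timing is not ignored, given the onset-interval table, the event counts, the person-years and the retention curves. That is true and narrows the gap, but none of these supplies a between-arm contrast free of retention.

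On follow-up, Protocol 12.4.1 requires SAEs to be reported to the sponsor through 30 days after the last dose. The same section has them recorded on the CRF only up to the last visit, so this hardly changes the tabulated SAEs. Protocol 17.3 suggests that subjects off drug may stay in the study, which sits awkwardly with Protocol 13.1, but the SAP's 9-day limit bounds the tables either way.

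Finally, a Cox model brings its own assumptions and will be imprecise for rare events. At 0.1/year about 13 SEP-363856 subjects would have an event (0.063 × 200). This stands, and is a reason to add the model beside the planned outputs, not in their place.

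**Conclusion.** The concern holds as a modest gap in the comparative analysis. The single between-arm AE estimate has no term for follow-up time in a trial whose own figures imply 40% one-year completion on the test drug. If retention differs, the odds ratio combines AE rate and retention and cannot tell them apart. Over the assumed range the distortion reaches at most 0.80 or 1.18, and it is always smaller than one standard error of the log odds ratio. These sizes rest on assumed hazards, assumed quetiapine XR retention, and dropout unrelated to AEs.

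A reader might go further and infer that the odds ratio is biased. The documents do not support that: they give no quetiapine XR completion figure, and with equal retention the illustrated distortion is zero. Nor is any confirmatory conclusion at risk, since the odds ratio is exploratory and its p-value nominal.

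The gap concerns all AEs, SAEs and EPS AEs. For AEs leading to discontinuation, the crude percentage is adequate and no further estimate is needed.

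**What to change.** Keep the crude tables and the odds ratio. Add to SAP 17.1.11, for all AEs, SAEs and EPS AEs:

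- a cause-specific Cox hazard ratio for time to first event, adjusted for geographic region (the factor already in the odds ratio model) and censored at the earlier of last dose + 9 days and last contact;
- cumulative incidence curves by arm, with discontinuation without the event as a competing event. Their end value should agree closely with the crude percentage, which serves as a check.

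Label any 1 − Kaplan-Meier curve as the hypothetical risk without discontinuation.

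The cost is SAP wording and a few more outputs from data already collected. The hazard ratio assumes proportional hazards, will be imprecise for rare SAEs, and compares on-treatment rates only. It should be read beside the crude tables and the retention Kaplan-Meier curves of SAP 9.

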7.2. Treatment Assignment and Blinding

7.2.1. Treatment Assignment

This is a randomized, double-blind, active comparator-controlled study.

Randomization will be stratified by country. The randomization schedule will be generated by a non-study biostatistician. Once a subject is deemed eligible to be randomized at Day 1, an IWRS will perform treatment assignment. Subjects will be randomized to one of the following treatment groups in a 2:1 ratio:

- Flexibly dosed SEP-363856 (50, 75, or 100 mg/day) for 52 weeks
- Flexibly dosed quetiapine XR (400, 600, or 800 mg/day) for 52 weeks

Once a randomization number has been assigned, it cannot be reused.

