2.2. STUDY ENDPOINTS

2.2.1. PRIMARY ENDPOINT

The primary endpoint is the incidence of overall AEs, SAEs, and AEs leading to discontinuation.

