3.2. METHOD OF ASSIGNING SUBJECTS TO TREATMENT GROUPS

The randomization schedule is generated by a non-study biostatistician.

The randomization is stratified by country and the randomization schedule is based on permuted blocks.

Once a subject is deemed eligible to be randomized at Day 1, an interactive web response system (IWRS) will perform treatment assignment. Subjects will be randomized to one of the following treatment groups in a 2:1 ratio:

- Flexibly dosed SEP-363856 (50, 75, or 100 mg/day) for 52 weeks
- Flexibly dosed Quetiapine XR (400, 600, or 800 mg/day) for 52 weeks

Once a randomization number has been assigned, it cannot be reused.

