7.2. MULTICENTER STUDIES

This study will be conducted by multiple Investigators at multiple centers in the US and non-US countries, including Russia, Romania, and Ukraine. Randomization is stratified by country.

When specified, statistical analysis will be adjusted for country.

Document: CCI

Author: PPD

Version Number: 0.6

Version Date: 30JAN2023

Template No.: CS_TP_BS016 Revision 6

Reference: CS_WI_BS005

Effective Date: 02Dec2019

A term for treatment-by-country interaction at Week 52/Visit 17 will be explored as part of the subgroup analysis (see [Section 16.1.1.4](#)). A significant interaction effect is defined as having a nominal p- value ≤ 0.10 . Additionally, graphical methods (i.e. Forest plots) will be used to present the analysis results separately for each country and to assess whether the interaction, if there is one, is quantitative (i.e. the treatment effect is consistent in direction but not in size) or qualitative (i.e. the treatment is beneficial for some but not for other countries).

Center pooling will not be implemented in the analyses for this study.

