16.1.6. PROPORTION OF SUBJECTS WHO ACHIEVE A RESPONSE

PANSS response is defined as a 20% or greater improvement (i.e. decrease) in PANSS total score from Baseline.

The percent change in PANSS total score from Baseline will be calculated by:

$$\frac{\text{PANSS total score at a visit or the Week 52 LOCF endpoint} - \text{PANSS total score at Baseline}}{\text{PANSS total score at Baseline} - 30} \times 100\%$$

For each subject, the responder indicator will be set to Y if the percent change is negative and the magnitude is equal to or greater than 20%. The indicator will be set to N if the percentage is negative but the magnitude is less than 20% or the percentage is non-negative. The indicator will be set to missing if the percentage is missing.

In addition, PANSS response defined by two more stringent thresholds will be assessed; that is, having a 30% or greater and 50% or greater improvement in PANSS total score from Baseline.

PANSS response at all three thresholds will be derived for all post-Baseline time points.

PANSS response at each scheduled visit and at the LOCF endpoint will be analyzed using a logistic regression model with responder indicator as the dependent variable and include factors for treatment and geographic region, and include Baseline PANSS total score as a covariate. The Number Needed to Treat (NNT) will be provided:

- The NNT for each SEP-363856 group will be derived as:

Document: CCI

Author: PPD

Version Number: 0.6

Version Date: 30JAN2023

Template No.: CS_TP_BS016 Revision 6

Reference: CS_WI_BS005

Effective Date: 02Dec2019

- $$\text{NNT} = \frac{1}{\text{Risk Reduction (RR)}} = \frac{1}{\text{PANSS Response Rate}_{\text{SEP-363856}} - \text{PANSS Response Rate}_{\text{Quetiapine XR}}}$$
- Only positive NNT results will be presented. The NNT results will be provided in whole numbers with any fractional values rounded up to the nearest whole number. The 95% CI of NNT will also be presented and are computed by taking the reciprocal of the 95% CI lower and upper bounds of the RR when both bounds are positive. The lower confidence limit will be rounded down to the largest whole number that is less than the computed estimate, and the upper confidence limit will be rounded up to the smallest whole number that is greater than the computed estimate.

The number and percentage of subjects who achieve a PANSS response will also be summarized descriptively by treatment group and visit.

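### The exploratory odds ratios for adverse events and for PANSS response adjust for US/Non-US although randomisation is stratified by country, which can pull the odds ratio towards 1 if the three non-US countries differ

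*SAP*

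**What the plan says.** Protocol 7.2.1 states: "Randomization will be stratified by country". SAP 3.2 agrees: "The randomization is stratified by country and the randomization schedule is based on permuted blocks". SAP 7.2 says the study runs "at multiple centers in the US and non-US countries, including Russia, Romania, and Ukraine", and SAP 7.1 lists country (four levels) and geographic region (US, Non-US) as separate factors.

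The two logistic models use region:

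- SAP 17.1.11, for all AEs, SAEs, AEs leading to discontinuation and extrapyramidal AEs: a "logistic regression model with treatment and geographic region as categorical factors".
- SAP 16.1.6, for PANSS response: the model will "include factors for treatment and geographic region, and include Baseline PANSS total score as a covariate".

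The PANSS MMRM (Protocol 15.3.5, SAP 16.1.1.1) and the PANSS ANCOVA (SAP 16.1.1.3) use country. So do the movement-scale models in SAP 17.6.2 to 17.6.4, which refer back to those two specifications.

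On status, SAP 2.2.1 says: "The primary endpoint is the incidence of overall AEs, SAEs, and AEs leading to discontinuation". Protocol 15.3.6.1 introduces the comparison with "As exploratory analyses, the odds ratios (OR) with 95% confidence intervals (CI) of all AEs, SAEs, AEs leading to discontinuation" and names no model. Neither 17.1.11, 16.1.6 nor the list of changes in SAP 3.7 explains why region was chosen.

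**The concern.** The usual rule is to analyse by the factor used to stratify randomisation. Here the analysis factor merges three of the four strata. Unlike a difference in means, an odds ratio is non-collapsible: leaving out a prognostic stratum moves the treatment odds ratio towards 1 relative to its value within strata, even with perfect balance. Ignoring part of the stratification also makes the test conservative.

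SAP 17.1.11 is the only place where the plan compares the arms on the three primary-endpoint components with an estimate, interval and p-value. In a safety comparison, movement towards 1 understates a difference in either direction, including one unfavourable to SEP-363856. The plan is also uneven within one topic: the extrapyramidal rating scales are adjusted for country, the extrapyramidal AEs only for region.

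SAP 9, 17.1 and 17.2 foresee discontinuations, AEs and local-laboratory use linked to the Russia-Ukraine conflict. That is a reason to think the non-US countries may not be alike, but it gives no rates.

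**Working it through.** **Inputs from the documents.** N = 300 allocated 2:1 (Protocol 15.1), so 300 × 2/3 = 200 on SEP-363856 and 100 on quetiapine XR; four countries; stratification by country; two-sided 5% (SAP 6.6). There is no plan figure to reproduce: the documents give no odds ratio, event rate, country share or power for these models.

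**Assumptions.** US share 40% or 10%, with the rest split equally over the other three countries; a common within-country odds ratio of 0.50; quetiapine XR event rates by country as shown, with 70% in the US for common AEs and 8% for SAE-type events.

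**Step 1: pooling the three non-US countries, by hand.** Take quetiapine XR rates of 30/50/70%. The odds are 0.4286, 1 and 2.3333. Halved, they are 0.2143, 0.5 and 1.1667, so the SEP-363856 rates are 0.1765, 0.3333 and 0.5385. With equal shares the mean rates are 0.3494 and 0.5000. The pooled odds ratio is (0.3494/0.6506)/(0.5/0.5) = 0.537, not 0.50. The same steps give 0.510 for 50/60/70% and 0.625 for 15/50/85%.

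**Step 2: adding the US stratum.** Within the US the odds ratio is 0.50, so the region-adjusted value falls between that and the pooled non-US value. The expected data were fitted once with treatment and region, once with treatment and country. Shrinkage is 1 − log(OR with region)/log(0.50). Power is Φ(z − 1.96) + Φ(−z − 1.96), with z = |log OR|/SE. The country model returns 0.500 throughout.

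| Non-US rates, quetiapine XR | US share | OR, region model | Shrinkage of log OR | Power, region vs country |
|---|---|---|---|---|
| 60/60/60% | 40% | 0.500 | 0% | 0.781 vs 0.781 |
| 50/60/70% | 40% | 0.506 | 2% | 0.767 vs 0.773 |
| 50/60/70% | 10% | 0.509 | 3% | 0.770 vs 0.780 |
| 30/50/70% | 40% | 0.523 | 6% | 0.727 vs 0.751 |
| 30/50/70% | 10% | 0.534 | 9% | 0.710 vs 0.748 |
| 15/50/85% | 40% | 0.574 | 20% | 0.598 vs 0.685 |
| 15/50/85% | 10% | 0.612 | 29% | 0.508 vs 0.641 |

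One row checked: |log 0.523|/0.253 = 2.56, and Φ(2.56 − 1.96) is about 0.73.

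The effect works in both directions. With a true odds ratio of 2.0 and 40% US, the region model gives 1.978, 1.907 and 1.723 for the three unequal patterns.

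**Step 3: rarer events (true odds ratio 0.50).** Non-US rates of 3/5/10% give 0.502 to 0.503, about 1% of the log odds ratio, with power 0.239 vs 0.240 at 40% US. Rates of 2/5/20% give 0.513 to 0.519, or 4-5%.

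**Step 4: type I error.** At a true odds ratio of 1 both models estimate 1.000. In 1,500 simulated trials per setting, rejection with region was 0.046, 0.041 and 0.025 for the modest, large and extreme patterns, against about 0.05 with country.

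**Step 5: sparse data.** With SAE rates of 3-10%, an ordinary four-country logistic fit showed separation in 19% of simulated trials at odds ratio 1 and 40% at 0.5; the region model did so in under 1%. Logistic regression conditional on country avoids most of this. With rates 5/3/5/10% (US first) and odds ratio 0.5, non-estimable fits were 0.9% (region) vs 0.8% (conditional), median odds ratio 0.487 vs 0.488, and power 17.9% vs 18.1%.

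The PANSS response model was not run separately. Its Baseline PANSS covariate may absorb part of any country difference.

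**The case against.** The strongest reply is that little depends on this. The odds ratios are exploratory, p-values are nominal (SAP 7.4), the protocol's hypothesis section (4.4) states no comparison, and the sample size rests on clinical considerations rather than power. The primary endpoint is reported as incidence by arm, which no logistic model touches. All of that stands and limits the weight of the point.

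The contrast with the rest of the plan is also not uniform. The rank ANCOVA for laboratory values, weight and BMI (SAP 17.2, 17.4), the log-rank tests (SAP 9, 16.2.12), Fisher's exact test (SAP 17.6.1) and the chi-squared tests (SAP 16.2.7) name no country term. SAP 7.2 promises country adjustment only where specified, and the AE subgroup summaries use region. So region may have been a deliberate choice. But those are unadjusted or baseline-only comparisons or descriptive tables; where the plan fits a parametric regression to a continuous outcome, it uses country. If region was deliberate, the reason is missing.

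Sparse data are a genuine argument for fewer levels, but only for the rare outcomes. They do not explain region for overall AEs or PANSS response.

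**Conclusion.** The mismatch is plain in the text and cheap to remove; its consequence is conditional and usually small. It needs both real differences among Russia, Romania and Ukraine and a true odds ratio other than 1. Under the assumed rates it is minor for modest differences, noticeable for large ones and material only for extreme ones. At a 40% US share the power cost is about 1, 2 and 9 points; at a 10% share it is about 1, 4 and 13. For rare SAEs it is close to nil.

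A reader might infer four stronger things that the documents do not support:

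- That country differences do dilute the odds ratio. No incidence by country is given.
- That the region-adjusted odds ratio is invalid. It is a less conditional estimand, attenuated relative to the within-country one, and type I error is not inflated.
- That the primary result is compromised. The incidence summaries by arm stand as they are.
- That every ANCOVA in the plan adjusts for country. The rank ANCOVA does not.

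**What to change.** In SAP 17.1.11 and 16.1.6, replace geographic region with country as the categorical factor.

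For sparse outcomes (SAEs, extrapyramidal AEs), specify a country-stratified sparse-data method in advance: conditional or exact logistic regression, or Mantel-Haenszel by country. Conditional regression copes with countries that have no events, but its estimate is still infinite if one arm has none, so name exact or Firth estimation for that case.

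The cost is a wording change, two more parameters in each model (four levels instead of two), and a second estimation method for rare events. If the sponsor prefers to keep region, the SAP should give the reason.
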